Once again, at the end of this visit, the subject will be asked to go to Investigational Drug Services (IDS) at University Hospitals in the Cleveland site where a study coordinator will dispense a 66-day supply (56 days plus 10 extra days) of either memantine capsules or identically-looking placebo capsules. For the 16-week duration of this study, capsules will be taken either once (first week) or twice daily (weeks 2-16) by mouth according to memantine's standard titration schedule. In the São Paulo site, a physician at the Hospital Israelita Albert Einstein (English: Albert Einstein Israelite Hospital)s will provide a 60-day supply of either memantine capsules or identically-looking placebo capsules, which will come randomized and prepackaged from the University of Iowa Pharmaceuticals Services.

Visits 4: Primary and Secondary Efficacy Measures at the 16th week from the start of the medication. Various aspects of the subjects' learning, memory, cognition, and adaptive behavior will be assessed again through the same neuropsychological test battery used in visit 2. Again, we expect that the test battery will take approximately two hours to administer. Therefore, two visits may be required to complete this series of assessments for a few participants. Again, for a subset of 30-60 participants in the Cleveland site, magnetic resonance imaging (MRI) of the brain will be performed at the Cleveland Clinic in the afternoon, one or two hours after the completion of the neuropsychological test battery.

Visit 5: Second and final follow-up medical visit at the 16th week from the start of the medication. The purpose of this visit is to ensure again that the study medication is being adequately tolerated. Similarly to visits 1 and 3, vital signs will be measured and a physical examination will be performed. Two blood samples again will be collected for checkup tests (here, the second blood sample is not optional!). In addition, a quantitative assessment of steady-state plasma levels of memantine and Alzheimer's disease biomarkers will be performed in the end of the study, after the unblinding of the randomization codes. The general procedures to be followed in this visit are listed below:

- Vital Signs
- Adverse Event Assessment
- Medication Compliance Check
- Complete Physical Exam
- Neurological Exam
- The Screen for Childhood Anxiety Related Emotional Disorders (SCARED)
- Concomitant Medication Check

HRP-503BIO	TEMPLATE: Biom	edical Protocol	

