In line with the relatively long half-life of the compound, the safety databases from the FDA and European Union do not list any signs or symptoms of withdrawal after discontinuation of memantine treatment; however, this issue has not been systematically evaluated. In addition, no cases of memantine abuse have been reported to date. However, the caregivers for all participants will be instructed in the consent form that the participants need to be referred to their primary care provider in the unlikely event of behavioral deterioration following discontinuation of memantine treatment in this study.

Describe when research procedures will take place and the duration of an individual subject's participation in the study. Use of the descriptive table listing the study procedures that indicates the visit/week of the interventions below is encouraged.

TABLE 1	SCREENIN G VISIT	VISIT 1	VISIT 2	VISIT 3	VISIT 4	VISIT 5
	Informal Interview, Informed Consent, EEG	Baseline Medical and Formal Screening	Baseline Neuropsych ological Evaluation, MRI	Week 8, Follow-up Medical Evaluation	Week 16, Final Neuropsych ological Evaluation, MRI	Week 16, Final Medical Evaluation
Explanation of Trial Procedures	Х					
Informed Consent/Assent	Х					
Medical History	Х	Х				
Electrophysiological Assessments	Х					X
Karyotyping	X (obtain copy of results if available)	X (collect blood if necessary)				
Physical Exam	,	X		Х		Х
Vital Signs		Х		Х		Х
Clinical Lab Tests		Х				X X
Screen for Childhood Anxiety Related Emotional Disorders (SCARED)		Х				Х
Pregnancy Test		X (blood)		X (urine)		X (urine)
ECG		Х				Х
Concomitant Meds	Х	Х		X		X
Adverse Events Monitoring				Х		Х
California Verbal Learning Test – CVLT II Short Form		_	X (AM)		X (AM)	
Spatial Span (CANTAB)			X (AM)		X (AM)	
Pattern Recognition Memory – PRM (CANTAB)			X (AM)		X (AM)	

HRP-503BIO	TEMPLATE: Biomedical Protocol		
Approved:	05/11/2018	Prior Version:	1/23/2018

Test of Receptive Grammar 2 – TROG-2	X (AM)	X (AM)
Par Associates Learning – PAL (CANTAB)	X (AM)	X (AM)
Recall of Digits (DAS-II)	X (AM)	X (AM)
Spatial working memory (CANTAB)	X (AM)	X (AM)
Matrices subtest of the (DAS-II)	X (AM)	X (AM)
Go-No Go task	X (AM)	X (AM)
Receptive vocabulary (PPVT-IV)	X (AM)	X (AM)
SIB-R	X (AM)	X (AM)
MRI Neuroimaging of a selected group of 30-60 participants	X (PM)	X (PM)
Medication Compliance Check	X	X

Ra

Radiation and Radioactive Substances	
1. Does the research involve the use of radiation or radioactive substances?	

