An "intention-to-treat" approach will be used in the statistical analyses, so that data from all subjects will be included regardless of subject eligibility or adherence to the protocol. The intent-to-treat (ITT) population is defined as all subjects who received at least one dose of medication and at least one evaluation at the start of double-blind treatment irrespective of compliance and protocol violations.

An "efficacy evaluable" population will be determined based on blinded application of protocol criteria, and a statistical assessment of this group will also be performed, and 80% or greater medication compliance and no major protocol violations will be required for a subject to be "efficacy evaluable." Repeated measures mixed models (MIXED) from SPSS will be used to deal with missed data.

Demographics and Baseline Characteristics

Demographic and baseline characteristics will be summarized by treatment, and simple comparisons of the mean numerical values of these characteristics between memantine and placebo groups will be performed using the two-tailed unpaired t test. Comparability of treatment groups at baseline will be tested for the efficacy parameters in the analysis of efficacy.

Efficacy Parameters

The two primary efficacy endpoints are the comparison of the effects of memantine and placebo on the California Verbal Learning Test II short form (CVLT-II short form). The CVLT-II short form score range is 0 to 36; the baseline and post-intervention scores of the participants

HRP-503BIO	503BIO TEMPLATE: Biomedical Protocol			
Approved:	05/11/2018	Prior Version:	1/23/2018	

with Down syndrome in our pilot study (Boada et al., 2012; APPENDIX 6) were 14.53 ± 1.80 and 20.12 ± 2.10 (mean \pm SEM), for the memantine arm, compared to 16.26 ± 1.82 and 13.74 ± 1.63 , for the placebo arm of the trial. (Higher score indicates better performance.) This measure is dependent on the functional integrity of temporal lobe structures such as the hippocampus. Improvement in performance in this measure is expected to be correlated to improvements in the individuals' ability to acquire skills requiring the use of declarative memory. Ultimately, in case we are able to confirm that the administration of memantine is indeed efficacious in improving this cognitive measure in this population, such gains may lead to a measurable improvement in the quality of life of persons with Down syndrome.

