Changes from baseline scores of the following secondary efficacy parameters at the post-baseline visit will also be used to compare the memantine and placebo groups:

- 1. Spatial Span (CANTAB)
- 2. Pattern Recognition Memory (PRM CANTAB)
- 3. Test for Reception of Grammar 2 (TROG)
- 4. Paired associates task (PAL CANTAB)
- 5. Recall of Digits subtest (DAS)
- 6. Matrices subtest (DAS)
- 7. Go-No Go test
- 8. Spatial working memory (SWM CANTAB)
- 9. Receptive vocabulary on the Peabody Picture Vocabulary Test-IV (PPVT-IV)
- 10. Scales of Independent Behavior-Revised (SIB-R)
- 11. Neurophysiological Assessments: Auditory Brainstem Response (ABR) Test and Mismatch negativity (MMN)
- 12. Brain morphometric Magnetic Resonance Imaging (MRI) of a subset of 30-60 participants will be performed for source localization for EEG evoked potential studies, quantitative hippocampal morphometry, and generation of hippocampal connectivity datasets.

Because the test scores of most participants in our pilot study were well below the standardized means of the adult versions of the neuropsychological instruments used here, we had to use the children's version of many of these instruments. We plan to do the same in the current study. Hence, instead of using the standard scores for most of the measures (which are based on the participant's age), all test scores will be expressed as "z-transformed" raw scores computed with sample mean and sample standard deviation (which will yields the Student's t-statistic for each measure). This method of standardization of the measures will allow us to compare drug effect across the various neuropsychological measures without changing the significance calculations for the drug effect on each individual measure.

It is very common in neuropsychology that each individual measure is typically subdivided into several sub-measures (sometimes more than a dozen sub-measures per test). Although eventually we plan to run comprehensive a posteriori analyses of the data to inform future studies, in the first report describing the analysis of the data of this trial, we intend to focus on the following sub-measures of the primary measure:

• California Verbal Learning Test II, short form: "Total Free Recall Discriminability" and "Free recall correct for learning trials".

HRP-503BIO TEMPLATE: Biomedical Protocol			
Approved:	05/11/2018	Prior Version:	1/23/2018

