To examine the relations among outcome variables, Pearson's r correlations for each time point will be computed across the whole sample. Point biserial correlation will be used to explore the relationship between the outcome variables and gender.

Statistical Models

For all continuous measures, therapeutic effects will be assessed using repeated measures mixed models (MIXED) from SPSS, including effects for treatment group, the baseline value (the covariance) and treatment by baseline interaction (if statistically significant), with change from baseline as the dependent variable. MIXED handles correlated data and unequal variances. Correlated data are very common in such situations as repeated measurements of survey respondents or experimental subjects. MIXED extends repeated measures models in generalized linear model (GLM) to allow an unequal number of repetitions. The other advantage of MIXED models is that it can handle missing data, which GLM repeated measures cannot. A to-be-named statistician from the Biostatistics, Epidemiology & Research Design core of the Case Western Reserve University Clinical & Translational Science Collaborative (CTSC) will be responsible for the analysis of the data from both the Cleveland and the São Paulo sites.

Confidentiality of Specimens and Banking

 \square I am not storing specimens in this research project – please leave the rest of this section blank

Describe:

- **☒** *The source of the specimens*
- ☑ Where the specimens will be stored
- ☑ How long the specimens will be stored
- ☑ *How the specimens will be labeled*
- ☑ How the specimens will be accessed
- ☑ Who will have access to the specimens
- ☑ When and how will the specimens be destroyed
- ☑ How will the specimens be transported (Please note if transporting specimens, a Material Transfer Agreement (MTA) is required).

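### With one post-baseline CVLT-II per subject, MIXED cannot deal with missing week-16 scores, and the plan does not say that the test is given to subjects who stop early

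*Combined protocol and SAP*

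**What the plan says.** **Analysis.** Study Populations states: "Repeated measures mixed models (MIXED) from SPSS will be used to deal with missed data". Statistical Models lists treatment group, baseline and a conditional treatment-by-baseline interaction, "with change from baseline as the dependent variable". It adds: "The other advantage of MIXED models is that it can handle missing data, which GLM repeated measures cannot". No pair term is named, although the section remarks that "MIXED handles correlated data and unequal variances" and the Replacement Policy describes the study as paired. No missingness assumption or sensitivity analysis is given.

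**Population.** Study Populations says that data from all subjects will be included. It defines the ITT set as "all subjects who received at least one dose of medication and at least one evaluation at the start of double-blind treatment", so no post-baseline score is needed to belong to it.

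**Schedule.** Table 1 marks the row "California Verbal Learning Test – CVLT II Short Form" at Visits 2 and 4 only. At Visit 4 subjects "will be assessed again through the same neuropsychological test battery used in visit 2". The week-8 visit (Visit 3) is medical. For the secondary measures, Efficacy Parameters refers to a single later visit: scores "at the post-baseline visit will also be used to compare the memantine and placebo groups".

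**Early stopping.** Study Design, Procedures and Timeline, and Withdrawal of Research Participants, give the Treatment Discontinuation Visit the same content as Visit 5, a medical visit with no CVLT-II. The Retrieved Dropout Visit is dated to when Visit 5 would have been, with no procedures listed. The paragraphs on dose tolerance and on serious adverse events describe subjects as dropped from the study, without saying whether they are still tested at week 16.

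**The concern.** A repeated-measures mixed model gains information about a dropout from that subject's other post-baseline records. Here there are none. The plan therefore claims a protection that its model does not have for the primary endpoint, and names no other. The inclusion of all ITT subjects is likewise not delivered: someone with a dose and a baseline evaluation but no week-16 score is in the ITT set and out of the estimate.

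Data collection matters more than wording, because an analysis can be rewritten later but a week-16 score that was never taken cannot be recovered. If subjects who stop early are not tested, the comparison rests on those who stayed, and its validity rests on an unstated assumption about why the others left.

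**Working it through.** **1. Outcome records per subject.** One post-baseline test and change as outcome give one row per subject and sub-measure:

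change = b0 + b1·arm + b2·baseline + error.

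Adding baseline to both sides gives

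week 16 = b0 + b1·arm + (b2 + 1)·baseline + error,

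so b1 is the same whether the outcome is change or the week-16 score. Check on a simulated trial of 200 with 27 missing week-16 scores: one-record REML, ANCOVA on change and ANCOVA on the week-16 score all gave 4.8213 (SE 0.7641), from the 173 observed subjects.

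**2. Would a pair term help?** In a check dataset of 100 pairs with 10 and 5 missing scores, 185 rows enter and 85 pairs are complete. A pair random effect keeps the 15 partners. Changing the dropouts' own baselines left its estimate at -0.172, so the dropouts themselves contribute nothing.

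**3. How many subjects?** The plan states no dropout rate for this trial. The pilot had 37 completers of 40 (Background, section 1.5): 3/40 = 7.5%, exact 95% CI 1.6% to 20.4%. For 200 subjects that is 15, with a range of 3 to 41.

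**4. Possible bias under no drug effect.** Let p be an arm's dropout proportion and d the amount by which the dropouts' mean change lies below the mean of everyone randomised to that arm. The observed mean is then too high by p/(1-p) × d, so

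bias = pM/(1-pM) × dM - pP/(1-pP) × dP (M memantine, P placebo).

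The SD of change is not in the documents. I assume 7. The pilot SEMs give single-visit SDs of 1.80 × √18 = 7.6, 2.10 × √18 = 8.9, 1.82 × √19 = 7.9 and 1.63 × √19 = 7.1, taking 18 on memantine (Risks to Research Participants) and 37 - 18 = 19 on placebo. Deficits of 0.5 to 1 SD (3.5 to 7 points) and all arm-specific dropout rates are also assumptions. With 90 and 95 analysed, SE = 7 × √(1/90 + 1/95) = 1.03. One-sided type I error = 1 - Φ(1.96 - bias/SE).

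| Dropout, memantine vs placebo | Deficit (SD) | Bias (points) | Type I error |
|---|---|---|---|
| 7.5% vs 7.5% | equal | 0 | 2.5% |
| 10% vs 5% | 0.5 in both | 0.0585 × 3.5 = +0.20 | 3.9% |
| 10% vs 5% | 1 in both | 0.0585 × 7 = +0.41 | 5.9% |
| 5% vs 10% | 0.5 in both | -0.20 | 1.5% |
| 5% vs 10% | 1 in both | -0.41 | 0.9% |
| 7.5% vs 7.5% | 1 vs 0.5 | 0.0811 × 3.5 = +0.28 | 4.6% |

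Here 0.0585 = 0.10/0.90 - 0.05/0.95 and 0.0811 = 0.075/0.925. Against the 4-point target, 0.20 to 0.41 is 5% to 10%. At SD 5 the 10% versus 5% bias is 0.15 to 0.29, and at SD 9 it is 0.26 to 0.53. In simulation, a pair random effect, or replacing some or all dropouts, left it at about 0.2 to 0.4.

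**5. Effect of testing dropouts at week 16.** If a random 50%, 70% or 90% of them are tested, the 10% versus 5% bias falls to 0.09-0.19, 0.05-0.11 or 0.02-0.04 points.

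**6. Power for 4 points, 200 falling to 185 analysed.** 98.0% to 97.2% at SD 7; 87.8% to 85.2% at SD 9.

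**7. When is the observed-score analysis valid?** Missingness depending only on arm and baseline is not quite enough. With a mean effect of 4, about 8% dropout driven by baseline alone, and an effect varying by 1 to 3 points per baseline SD, simulated ANCOVA without the interaction averaged about 4.1 to 4.3. Fitting the interaction with baseline centred at the all-randomised mean gave about 4.0.

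**The case against.** **The collection gap is partly silence.** This stands. Visit 5 content is assigned only to the Treatment Discontinuation Visit. The Retrieved Dropout Visit is separate, and its content is unstated rather than restricted. Nothing expressly cancels Visit 4 for someone who stops medication but stays in the study, and the case report form is a separate document. A reader might infer that the plan omits the CVLT-II for dropouts. The text supports only that it does not say.

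**A pair term may be intended.** The list of effects need not be exhaustive, and the study is called paired. A pair random effect would keep a dropout's partner, whom a paired test would lose, so the missing-data sentence would then have some content. It would still not supply the dropout's own outcome.

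**Replacement covers it.** The Replacement Policy restores numbers, except after a severe adverse event, but not the outcomes of those who left.

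**Dropout may be balanced.** It may. Risks to Research Participants reports equal adverse-event discontinuation in dementia trials, which is a different population, and three pilot dropouts show neither balance nor imbalance. A reader might infer that the result will be biased towards memantine. The documents do not support that: the sign follows the assumed imbalance, and the bias is zero when rates and deficits are equal.

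**Conclusion.** The point holds for the primary endpoint. With the listed effects, MIXED is equivalent to ANCOVA on observed week-16 scores, so the claims that it deals with missing data and that every ITT subject is included are not delivered. The text also leaves open whether the week-16 CVLT-II is sought after early stopping.

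The numerical consequence is conditional. Under the assumptions above it ranges from nothing to about 0.4 points either way, with little loss of power. It would be too strong to call the analysis invalid. It is sound if missingness depends only on arm and baseline and the baseline relationship, including any interaction, is correctly modelled. The fault is that this is unstated, unexamined and presented as solved. It should be fixed while week-16 scores can still be collected.

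**What to change.** 1. **Collection.** State that the week-16 CVLT-II is sought from every randomised subject whatever the treatment status, unless consent is withdrawn. It would be given at Visit 4 or the Retrieved Dropout Visit, as far as possible under the testing conditions in Duration of the Testing Procedure and Quality Control. Say that this includes subjects described as dropped. No treatment-stopping rule changes.

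2. **Analysis text.** In Study Populations and Statistical Models, keep change from baseline as the outcome and replace the missing-data claim with: *The primary analysis uses all subjects with a week-16 score, including retrieved dropouts and, where a subject was replaced, both that subject and the replacement. Subjects without a week-16 score do not contribute. The analysis assumes that missingness depends only on arm and baseline and that the baseline relationship, including any treatment-by-baseline interaction, is correctly modelled. If the interaction is included, baseline is centred at the mean of all randomised subjects.* Name the pair term if one is intended.

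3. **Sensitivity.** Prespecify one analysis of departures from that assumption, for example delta-adjusted multiple imputation.

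**Cost.** One short test session for about 15 people if attrition matches the pilot, possibly on a separate morning and without the full battery order, plus one extra analysis and the wording changes.

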1.6. A follow-up, phase II clinical trial of memantine in adolescents and young persons with Down syndrome. Because of the promising findings on our pilot study (Boada et al., 2012; APPENDIX 6) with young adults, all the professionals involved in the present project agreed that these findings were encouraging enough, and the risks were small enough, that a follow-up, larger trial was warranted. We are proposing to use the short form of the CVLT-II as the primary efficacy measure in this new study. The main goal of this study is to repeat the same treatment (drug, drug dose, and treatment duration) of the previous study on a larger sample to test whether the memantine treatment indeed produces a significant improvement on this important measure of hippocampusdependent cognitive performance. Given the P-value <0.10 for the Recall of Digits test, which is potentially a measure of prefrontal cortex-mediated short term memory, we also decided to add two new prefrontal cortex dependent tasks to the new study: the Spatial span from the CANTAB battery, and a simple Go/No-go test. In addition, in this expanded study, we plan to investigate the usefulness of the electrophysiological measure known as mismatch negativity (MMN), as a biomarker of the severity of the cognitive disability in a person with Down syndrome as well as a potential surrogate marker for the efficacy of memantine in persons with Down syndrome. This is a non-invasive, easy to implement test, which involves electroencephalographic (EEG) assessment of the brain wave that occurs after any discriminable deviation in an ongoing repetitive acoustic stimulation with identical tones. The choice of MMN comes from several studies showing that the MMN amplitude is sensitive to modulation of NMDA receptors by pharmacological treatments with the NMDA receptor antagonists such as ketamine (Umbricht et al., 200), phencyclidine, MK-801 (Steinschneider et al., 1996), and memantine (Nikulin at al., 2007; Tikhonravov et al., 2010).

Please add relevant references at the end of the protocol, not at the end of this section.

Inclusion and Exclusion Criteria

- 1. Describe how individuals will be screened for eligibility.
- 2. Describe the criteria that define who will be **included** in your final study sample.

	Inclusion
1.	Subjects will be males or females with Down syndrome aged 15 to 32 years.
2.	The cytogenetic diagnosis should be either "Trisomy 21", or "Complete

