The primary efficacy measure is focused on episodic memory. The choice of the appropriate measure for individuals with Down syndrome was based on results of our pilot clinical trial of the drug memantine in young adults with Down syndrome (Boada et al., 2012; APPENDIX 6). We hypothesize that treatment with memantine will produce significant improvements in the California Verbal Learning Test-II (CVLT-II) short form. The CVLT-II score range is 0 to 36; the baseline and post-intervention scores of the participants with Down syndrome in our pilot study (Boada et al., 2012) were $14.53 \pm$ 1.80 and 20.12 ± 2.10 (mean \pm SEM), for the memantine arm, compared to 16.26 ± 1.82 and 13.74 ± 1.63 , for the placebo arm of the trial. (Higher score indicates better performance.) As aforementioned, this measure is dependent on the functional integrity of temporal lobe structures such as the hippocampus. Improvement in performance in this measure is expected to be correlated to improvements in the individuals' ability to acquire skills requiring the use of declarative memory. Ultimately, in case we are able to confirm that the administration of memantine is indeed efficacious in improving this cognitive measure in this population, such gains may lead to a measurable improvement in the quality of life of persons with Down syndrome.

Secondary Efficacy Measures

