 - Labs (including pregnancy test for females of childbearing potential)

Visit 2: Baseline neuropsychological assessments will occur one to three weeks after Visit 1. These tests are designed to evaluate the cognitive skills of the participants before the start of the medication. A battery of tests to assess non-verbal reasoning abilities, memory, vocabulary, and language skills will be administered by a trained psychologist. In these interactive tests the participant will be asked to point at a picture, word, or number in response to different requests by the examiner (see description of

HRP-503BIO	TEMPLATE: Biom	edical Protocol	
Approved:	05/11/2018	Prior Version:	1/23/2018

"primary and secondary efficacy measures"). In addition, the participant will be asked to perform a few user friendly computer-based tests. The guardian/parent will be asked to complete a questionnaire about the participant everyday behavior and general abilities (the Scales of Independent Behavior Revised - SIB-R). Because we expect the test battery will take approximately two hours to administer, two visits may be required to complete this series of assessments for a few participants. In the next section, we provide a description of the neuropsychological test battery used in this trial. Below is a complete list of the psychometric tests that will be used:

- California Verbal Learning Test II Short Form (CVLT-II)*
- Spatial Span (from the CANTAB)
- Pattern Recognition Memory (PRM CANTAB)
- Test for Reception of Grammar 2 (TROG-II)
- Paired associates task (PAL CANTAB)
- Recall of Digits subtest (DAS)
- *Matrices subtest (DAS)*
- Go-No Go test
- Spatial working memory (SWM CANTAB)
- Receptive vocabulary on the Peabody Picture Vocabulary Test-IV (PPVT-IV)
- Scales of Independent Behavior-Revised (SIB-R)

* Trial primary measure

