3.3. Neuropsychological Test Battery

The battery will include measures to assess skills in five major areas: a) memory functioning; b) intellectual functioning; c) language and vocabulary; d) visual and verbal working memory; and e) adaptive/behavioral functioning. The battery includes measures that we expect may be sensitive to changes caused by memantine, given the hypothesized mechanism of action of the drug and previous results from a pilot trial (Boada et al., 2012; APPENDIX 6). Specifically, we hypothesize that the participants will improve in their test scores for declarative memory and, potentially, for working memory capabilities. We have also selected measures of receptive semantics and grammatical understanding that we predict will remain relatively stable, thus acting as benchmark, discriminant measures. Lastly, we have included a comprehensive measure of adaptive functioning that also measures the presence, frequency, and severity of 8 core emotional/behavioral problems. A secondary hypothesis is that memantine may decrease the frequency or severity of behavioral difficulties, although we found no indication of this potential in the previously mentioned pilot trial. All the measures of this battery have been used in research with persons with Down syndrome, and have adequate psychometric properties. What follows is a list of measures, by domain, and a brief description of each.

Memory functioning

A) California Verbal Learning Test-II (CVLT-II) - Short Form: This test is the primary efficacy measure of this clinical trial. It assesses supraspan word learning ability as an index of episodic verbal long-term memory. This type of test is known to be sensitive to posterior hippocampal functioning based on neuroimaging, and has also been shown to be impaired in populations with degeneration or damage to the hippocampus. Participants are provided with an orally presented list of words which are repeated over 5 trials. Short and long delay recall trials as well as a recognition trial follow. The delay interval is 10 minutes. Two dependent variables were selected, based on prior literature,

HRP-503BIO	TEMPLATE: Biomedical Protocol		
Approved:	05/11/2018	Prior Version:	1/23/2018

as indexing hippocampal function: Total number of target items correct summed across learning trials 1-4, and total free recall discriminability for the learning trials, which takes into account hits as well as false positives.

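### Two scores on the CVLT-II short form are declared primary, but the plan does not say which must succeed or at what alpha

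*Combined protocol and SAP*

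**What the plan says.** Most of the protocol speaks of one primary measure. Section 1.6 proposes the "short form of the CVLT-II as the primary efficacy measure in this new study". The Primary Efficacy Measure section opens with "The primary efficacy measure is focused on episodic memory". The Visit 2 test list stars the CVLT-II as "Trial primary measure". Section 3.3 says "This test is the primary efficacy measure of this clinical trial".

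The same paragraph of section 3.3 then selects two dependent variables from that test. One is "Total number of target items correct summed across learning trials 1-4". The other is a discriminability score, given as "total free recall discriminability for the learning trials, which takes into account hits as well as false positives". In the statistical section, Efficacy Parameters states "The two primary efficacy endpoints are the comparison of the effects of memantine and placebo on the California Verbal Learning Test II short form". It goes on to describe one score with a 0 to 36 range and one set of pilot means. Near its end it says of the first report that "we intend to focus on the following sub-measures of the primary measure", and lists free recall discriminability and free recall correct for the learning trials.

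Sample Size gives about 99.9% power at 100 subjects per group for a 4-point between-group difference in change on the CVLT-II short form, with a one-tailed paired design and alpha 0.025. It does not say which of the two scores is meant. Statistical Models applies one mixed model to every continuous measure and gives no alpha, sidedness or multiplicity rule.

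**The concern.** Section 1.6 presents the trial as a larger test of a pilot signal on this instrument, and Sample Size speaks of confirming or rejecting that signal. This needs a rule for calling the trial positive. With two declared primary endpoints there are four possible outcomes, and the plan gives no reading for the two in which only one score succeeds.

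The error rate is also left open. One alpha was set for one difference. If it is applied to each score and either success is taken as confirmation, the chance of a false confirmation exceeds the 2.5% used to size the trial. The choice would also be made after the results are known.

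**Working it through.** **1. The plan's own power figure, for one score.** Inputs from Sample Size: 100 pairs, difference 4, one-sided alpha 0.025, paired design. For a paired t test the noncentrality is 4√n/SD, where SD is that of the within-pair difference in change. No SD is stated, so the figure cannot be reproduced from stated inputs. Solving backwards:

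- 99.9% at 100 pairs implies SD 7.84. That SD gives 97.3% at 60 pairs, against the stated figure of about 99%.
- 99% at 60 pairs implies SD 7.11.

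A cross-check uses the pilot standard errors in Efficacy Parameters. I took 18 memantine participants (the denominator under Risks to Research Participants) and 37 − 18 = 19 placebo completers (37 is in section 1.5; the split is inferred).

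- Memantine SDs: 1.80√18 = 7.64 and 2.10√18 = 8.91.
- Placebo SDs: 1.82√19 = 7.93 and 1.63√19 = 7.11.
- Change variance in each arm is a² + b² − 2rab, where a and b are the baseline and follow-up SDs and r is the assumed baseline-to-follow-up correlation.
- At r = 0.7 this is 42.4 and 34.5. With no within-pair correlation, SD = √(42.4 + 34.5) = 8.77.
- Likewise SD = 10.09 at r = 0.6 and 7.22 at r = 0.8.

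The stated power is therefore plausible, but it describes one score only.

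**2. Error if either score may win.** Suppose each score is tested at one-sided 0.025 and memantine affects neither. Then

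P(at least one rejects) = 2 × 0.025 − Φ₂(−1.96, −1.96; ρ),

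where Φ₂ is the bivariate normal distribution function and ρ is the correlation between the two test statistics.

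| ρ (assumed) | Φ₂: both reject | Either rejects |
|---|---|---|
| 0 | 0.06% | 4.94% |
| 0.5 | 0.46% | 4.54% |
| 0.7 | 0.83% | 4.17% |
| 0.9 | 1.48% | 3.52% |
| 0.95 | 1.77% | 3.23% |
| 0.99 | 2.17% | 2.83% |

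A high ρ is plausible, because both scores come from the same learning trials and discriminability counts the hits. The documents give no value.

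**3. Error under an explicit rule.**

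- Fixed order: the second score is tested only after the first rejects, so the rate is at most 2.5%.
- Alpha 0.0125 per score: at most 2 × 0.0125 = 2.5%; 2.15% at ρ = 0.7 and 1.43% at ρ = 0.99.
- Both required at 0.025: the middle column of the table when neither score is affected, and never above 2.5%.

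**4. Power per score at alpha 0.025 and 0.0125.** Recruitment Methods gives 50 per arm for Cleveland alone; Sample Size uses 60.

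| SD of pair difference | 100 pairs | 60 pairs | 50 pairs |
|---|---|---|---|
| 7.84 (implied by 99.9%) | 99.9% → 99.7% | 97.3% → 94.8% | 94.3% → 89.9% |
| 10.09 (r = 0.6) | 97.5% → 95.3% | 85.6% → 77.7% | 78.5% → 68.8% |
| 8.77 (r = 0.7) | 99.5% → 98.8% | 93.5% → 88.8% | 88.5% → 81.6% |
| 7.22 (r = 0.8) | 99.98% → 99.9% | 98.8% → 97.5% | 97.0% → 94.3% |

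These are approximations. The model under Statistical Models has no pair term and adjusts for baseline, which would reduce the SD somewhat.

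**5. Power if both scores must win.** Assume equal standardised effects and ρ from 0.7 to 0.99. SD 10.09 gives 96.0–97.3% at 100 pairs and 69.6–77.0% at 50. SD 8.77 gives 99.1–99.4% and 83.0–87.7%. At SD 7.22 and 50 pairs, joint power lies between 2 × 0.970 − 1 = 94.0% and 97.0%.

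**The case against.** A reader might infer that the protocol contradicts itself by naming one primary measure in some places and two primary endpoints in another. The documents largely answer that. Section 3.3 calls the test the primary measure and selects two variables from it in the same paragraph, and Efficacy Parameters calls these sub-measures of the primary measure. One instrument with two named scores is a coherent reading. It does not settle how the two scores are to be judged together.

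A reader might also infer that the trial runs at 2.8–4.2% against a promised 2.5%. The documents do not support that. The 0.025 appears only as a sample-size input and is never called the trial-wide level. No section says that a win on either score suffices, and no correlation is given. If one-tailed 0.025 was meant as half of an overall 0.05, the either-wins rate stays within that total at any correlation. Even then, the intention needs to be written down.

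Nor is this a free choice among many CVLT-II sub-scores, since both are prespecified by name. The single 0–36 score in Efficacy Parameters, and a 4-point difference on that scale, point towards items correct as the score that was powered. That is a reasonable inference, but Sample Size does not say so.

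Finally, this is a phase II trial with two overlapping scores, so any inflation is modest. That limits the seriousness of the point without filling the gap.

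**Conclusion.** The gap is real and limited. Two primary endpoints are declared, one alpha is tied to one unnamed score, and no success rule exists. The firm consequence is that a result on only one of the two scores is undefined.

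The inflation is conditional. It requires testing each score at one-sided 0.025, counting either success, and intending 2.5% overall. It is then 0.3 to 1.7 percentage points at assumed correlations of 0.99 to 0.7, and at most 2.4 points, at zero correlation. It disappears if both scores must succeed. The point should be corrected, but it does not undermine the design.

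**What to change.** Before unblinding, amend Efficacy Parameters and Statistical Models to state the alpha and sidedness of the final tests and to test the two scores in fixed order at one-sided 0.025. The first should be the score that the sponsor confirms was used for the 4-point power calculation; the other is tested only if the first succeeds. Aligning the wording on measure, endpoint and sub-measure can be done in the same amendment. It is a text change with no new participants or data. Power for the first score is unchanged; the cost is that the second score alone cannot make the trial positive.

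Two alternatives also hold the error at or below 2.5%:

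- **0.0125 per score.** At 100 pairs, power per score falls from 99.9% to 99.7% at the SD implied by the stated power, or from 97.5–99.98% to 95.3–99.9% across the pilot-derived SDs (r = 0.6 to 0.8). At 50 pairs, should only Cleveland contribute, the pilot-derived range falls from about 78–97% to 69–94%.
- **Both scores required at 0.025.** The stated power for one difference would then no longer describe the chance of success, and joint power should be calculated and reported.

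The sponsor should choose one rule and record it.
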